**3.0 PRELIMINARY DATA ANALYSIS OF DEEPER COOLING**

**3.1 Preliminary data analysis performed for this protocol:** Preliminary analysis of data from the randomized control trial ([name] 05) was carried out in an attempt to optimize cooling strategies for the current protocol. Neonates being cooled on the servo controlled mechanism of the Blanketrol Hyper-Hypothermia cooling system do drop their core esophageal temperature initially below target temperature (overshoot of temperature) for varying periods of time before they reach equilibrium defined as within 0.1-0.2 of target ([name] 08). We examined details of recorded temperatures of all cooled infants and performed three analyses of the whole body hypothermia trial.

- 1) The first analysis was to evaluate whether there was an association between time spent below target temperature (< 33.5°C) and primary outcome. As noted in Table 2 below, there was no significant association between times spent below 33.5°C and primary outcome, or components of the primary outcome, among infants in the hypothermia group; however there is a trend for a lower frequency of primary outcome with greater time spent < 33.5°C. One explanation for lack of a significant association could be that time spent below 33.5°C in this study was not adequate enough, hence there is a need to examine whether deeper and longer cooling is neuroprotective.

**Table 2:** Hypothermia infants – Hours spent with esophageal temperature < 33.5

	N	Mean	SD	Q1	Median	Q3	p-value†
All infants	101*	48.72	18.71	36	52	63.25	-
Death or mod-severe disability	44	45.44	21.27	31.25	48.25	60.5	0.22
Infants without primary outcome	57	51.25	16.21	39.75	52.25	65	
Death	23	42.26	23.78	15.25	45.75	59	0.18
Survival	78	50.62	16.64	37.5	52.875	64.5	
Among survivors							
Mod-severe disability	21	48.92	18.06	33.5	54	61	0.54
No mod-severe disability	57	51.25	16.21	39.75	52.25	65	

\*One infant had missing esophageal temperatures. Q represents quartiles. N = number of infants. Mean and Median is time in hours.

† P-values are from Wilcoxon Two-Sample Test, t approximation.

2. A second analysis was performed to understand why some infants in the hypothermia group had excessive decreases in temperature (either following the initial overshoot or after achieving equilibration) because this information may enable us to target specific approaches among those infants who we have predicted would tolerate deeper temperatures less well. We compared the perinatal characteristics (age of randomization, 10 minute Apgar score, cord pH, and base deficit) and neonatal characteristics (birth weight, seizures at randomization, level of encephalopathy and inotropic support at randomization) between infants who had no temperatures recorded below 32°C after the initial overshoot compared to those infants who had a temperature of less than 32°C after the initial overshoot and those who had a temperature of < 32°C after achieving equilibration. As noted in Table 3, there were no significant differences between the infants who did not have an overshoot below 32°C and those who dropped their temperatures < 32°C after the overshoot or after equilibration. *There is however a trend for a greater need for inotropic support at randomization between those infants who dropped their temperature below 32°C after initial overshoot (7/17 or 41%) and those who dropped their temperatures after equilibration (6/10 or 60%) compared to those who had no drops below 32°C (20/74 or 27%).*

**Table 3:** Hypothermia infants—comparison of infants with esophageal temperatures < 32°C after initial overshoot or equilibration.

	No drops below 32°C after initial overshoot (N=74)		Esop. temp. < 32°C after initial overshoot (N=17)		Esop. temp. < 32°C after equilibration (N=10)		p-value (Fisher's Exact Test)
	N	%	N	%	N	%	
Outborn	34	46%	9	53%	4	40%	0.85
Male gender	36	49%	12	71%	3	30%	0.11
10 minute apgar ≤ 5 *	59	86%	11	73%	9	90%	0.52
Seizures at randomization	30	41%	10	59%	4	40%	0.38
Severe level of initial HIE †	22	30%	6	35%	3	30%	0.94
Moderate level of initial HIE	51	70%	11	65%	7	70%	
Inotropic support at randomization	20	27%	7	41%	6	60%	0.08

\* 7 infants are missing this data, N=94. Five are in the first group (N=69), and two are in the middle group (N=15). † 1 infant is missing initial HIE in the first group (N=73).

490  
 491  
 492  
 493  
 494  
 495  
 496  
 497  
 498  
 499

3. Lastly, variables were examined between infants who had no decreases in esophageal temperature below 32°C with those who had decreases after either overshoot or after equilibration (Table 4). *As noted, infants with a lower birth weight (when weight is evaluated as a continuous measure) had more frequent decreases in temperature below 32°C.*

**Table 4:** Hypothermia infants: Comparison of infant with esophageal temperatures < 32°C after initial overshoot or equilibration.

Age at randomization	N	Mean	SD	Min	Q1	Median	Q3	Max	p-value
No < 32°C after overshoot	74	4.29	1.27	0.77	3.5	4.48	5.1	7.33	0.87
< 32°C after overshoot	17	4.27	1.34	2.08	3.5	4.25	5.53	6.42	
< 32°C after equilibration	10	4.06	1.26	2.2	3.25	3.92	5.23	5.58	

500

Birth weight	N	Mean	SD	Min	Q1	Median	Q3	Max	p-value
No < 32°C after overshoot	74	3475.9	642.8	2050	3020	3322	3860	5432	0.04
< 32°C after overshoot	17	3153.8	484.8	2570	2761	3100	3461	4110	
< 32°C after equilibration	10	3108.6	499.9	2430	2755	2960.5	3510	3960	

501

Cord pH	N	Mean	SD	Min	Q1	Median	Q3	Max	p-value
No < 32°C after overshoot	54	6.87	0.20	6.55	6.71	6.89	6.99	7.27	1.0
< 32°C after overshoot	10	6.84	0.17	6.47	6.78	6.89	6.98	7.02	
< 32°C after equilibration	8	6.87	0.15	6.69	6.78	6.88	6.91	7.19	

502

Cord base deficit	N	Mean	SD	Min	Q1	Median	Q3	Max	p-value
No < 32°C after overshoot	45	18.38	7.36	3	14	18	23	34	0.95
< 32°C after overshoot	9	18.33	4.5	10	16	20	21	24	
< 32°C after equilibration	8	19.25	4.80	12	16	18.5	24	25	

503 \* P-values are from Kruskal-Wallis Test (one-way ANOVA). Variables tested are  
504 continuous measures

505

506 *Therefore, in the current protocol it will be necessary to identify those infants at higher*  
507 *risk for temperature decreases below target (infants requiring blood pressure support*  
508 *and those <25th percentile for weight) and an algorithm will be developed to control*  
509 *target set point temperatures in these infants.*

510

511 **3.2 Current status of trials evaluating cooling for HIE initiated < 6 hours of age:** The  
512 current management of encephalopathy in the NICHD Neonatal Network Centers is to  
513 provide whole body cooling to 33.5°C for 72 hours. Centers in the Cool Cap study  
514 currently offer selective head cooling at all centers. The Total Body Cooling (TOBY)  
515 trial recruited 325 infants and demonstrated that among survivors, cooling resulted in  

## 531 **4.0 STUDY DESIGN**

532

533 This will be a prospective, randomized, 2 X 2 factorial design multi-center trial  
534 conducted by the NICHD Neonatal Research Network. The individual factors to be tested  
535 will be:

- 536 1) A prospective comparison of 2 cooling durations (72 vs.120 hours)
- 537 2) A prospective comparison of 2 different depths of cooling (esophageal  
538 temperatures of 33.5°C vs. 32.0°C)

539

### 540 **4.1 Primary Hypothesis:**

- 541 1) Relative to infants receiving whole body cooling for 72 hours, cooling for 120  
542 hours will reduce death or disability
- 543 2) Relative to infants receiving whole body cooling at an esophageal temperature of  
544 33.5°C, cooling to an esophageal temperature of 32.0°C will decrease death or  
545 disability

546 **4.2 Secondary Hypotheses:**

- 547 1) There will be no statistical interaction between the two factors tested in this trial  
548 2) Cooling to a greater depth and/or longer duration will result in the following:  
549 a. No increase in acute adverse events among infants cooled for 120 hours  
550 b. No increase in acute adverse events among infants cooled to 32.0°C  
551 c. Mean Cognitive score at 18-22 months of age will be higher among infants cooled  
552 for 120 hours  
553 d. Mean Cognitive score at 18-22 months will be higher among infants cooled to  
554 32.0°C  
555

556 A factorial design has been selected because the conditions are ideal for such an approach  
557 (Piantadosi 05). Namely, the interventions can be administered together without  
558 significantly changing the intensity/magnitude of each in the presence of the other. In  
559 addition, there is interest in learning about the effect of the two combined interventions  
560 on outcome, and large statistical interactions between the 2 treatments (longer cooling,  
561 deeper cooling) are not anticipated. The mechanisms of neuroprotection associated with  
562 longer or deeper cooling are likely to be similar to mechanisms associated with  
563 neuroprotection using shorter or lesser degrees of hypothermia but may differ in the  
564 extent of mechanisms involved.  
565

566 Since safety and feasibility of cooling infants with HIE to the duration and depth  
567 proposed in this study has not been performed to date, the Data Safety Monitoring  
568 Committee (DSMC) of the NRN will examine data after the first 40 subjects (10 in each  
569 arm of the factorial design) are randomized into the proposed study. Enrolment will be  
570 temporarily halted while the DSMC reviews the first interim analysis for safety and will  
571 be resumed after the DSMC, on review of this data, decides that recruitment may  
572 commence. This approach is similar to the first RCT of whole body hypothermia  
573 performed by the NRN in 1998 where 20 infants were cooled to 34.5°C vs. control with  
574 no adverse events ([name] 02) before the whole body hypothermia trial was initiated  
575 with cooling to 33.5°C.  
576

577 **4.3 Inclusion Criteria:** The inclusion criteria are similar to the first whole body  
578 hypothermia for HIE trial ([name] 05). All infants with a gestational age  $\geq 36$  weeks  
579 will be screened for study entry if they are admitted to the NICU with an admitting  
580 diagnosis of fetal acidosis, perinatal asphyxia, neonatal depression or encephalopathy.  
581 Infants will be evaluated by physiological criteria, followed by a neurological  
582 examination. Eligibility criteria will include a pH  $\leq 7.0$  or a base deficit  $\geq 16$  mEq/L  
583 on umbilical cord or any postnatal sample within 1 hour of age. If, during this interval, a  
584 pH is between 7.01 and 7.15, a base deficit is between 10 and 15.9 mEq/L, or a blood gas  
585 is not available, additional criteria will be required. These include an acute perinatal  
586 event and either a 10-minute Apgar score  $\leq 5$  or assisted ventilation initiated at birth and  
587 continued for at least 10 minutes. Once these criteria are met, all infants will have a  
588 standardized neurological examination performed by a certified physician examiner.  
589 Infants will be candidates for the study when encephalopathy or seizures are present.  
590 Encephalopathy will be defined as the presence of 1 or more signs in 3 of the following 6  
591 categories: 1) level of consciousness: lethargy, stupor or coma; 2) spontaneous activity:

decreased, absent; 3) posture: distal flexion, decerebrate; 4) tone: hypotonia, flaccid or hypertonia, rigid; 5) primitive reflexes: a) suck, weak, absent; b) Moro, incomplete, flaccid; and 6) autonomic nervous system: a) pupils: constricted, unequal, skew deviation or non reactive to light; b) heart rate: bradycardia, variable heart rate or c) respiration: periodic breathing, apnea. Infants will be classified as moderate or severe encephalopathy based on a predefined algorithm. Determination of the stage of encephalopathy will be based on a modified Sarnat stage by scoring the presence of moderate or severe abnormalities in 6 categories. The number of moderate or severe signs determines the extent of encephalopathy and if signs are equally distributed the designation of moderate or severe encephalopathy will be based on the level of consciousness. Multiple births will be enrolled in the same arm of the study.

**4.4 Exclusion Criteria:** Exclusion criteria will include the following: a) inability to randomize by 6 hours of age, b) major congenital abnormality, c) major chromosomal abnormality (including Trisomy 21), d) severe growth restriction ( $\leq 1800$ gm birth weight), e) infant is moribund and will not receive any further aggressive treatment, f) refusal of consent by parent or g) refusal of consent by attending neonatologist. In addition, infants with a core temperature  $< 32.5^{\circ}\text{C}$  for  $\geq 2$  hours at the time of randomization by the research team would not be eligible for the study.

**4.5 Randomization and Stratification:** After informed consent is obtained, infants with moderate /severe encephalopathy will be randomized to either usual depth of cooling (at  $33.5^{\circ}\text{C}$ ) or deeper cooling (at  $32.0^{\circ}\text{C}$ ), and then to usual length of cooling (for 72 hours) or longer cooling (for 120 hours). This double randomization will create the four groups shown in **Figure 2** below.

**Figure 2:** Design outline of proposed trial

		Depth of Cooling		Margin
		33.5°C (Group A)	32.0°C (Group B)	
Duration of Cooling	72 hours (Group X)	AX	BX	X
	120 hours (Group Y)	AY	BY	Y
Margin		A	B	

Randomization will be conducted using permuted block design and stratified by clinical site and stage of encephalopathy. Telephone randomization will occur 24 hours a day, 7 days a week, by the Data Coordinating Center at RTI International, Research Triangle Park, NC. Randomization should occur within 6 hours of age. Cooling will occur at  $< 6$  hours for all eligible infants since this is usual care at all NRN sites.

**4.6 Intervention:** Care-givers will not be masked to therapy. All infants will be cooled using the Cincinnati Sub-Zero Hyper-Hypothermia Blanketrol System. An esophageal temperature probe will be placed in the lower third of the esophagus and the probe will be

630 interfaced with the Blanketrol System. The esophageal temperature will be controlled in  
631 the automatic control mode (“servo”) at the target temperature for the duration of cooling.  
632 At the completion of cooling, the control set point will be increased 0.5°C per hour until  
633 the esophageal temperature is  $\geq 36.5$  °C for four hours. Once achieved, the esophageal  
634 probe will be removed, the infant will be taken off the cooling/heating blanket, and  
635 continued temperature control will be adjusted per skin temperature if servo- controlled,  
636 or environmental temperature if in an incubator (not on servo) to maintain temperature  
637 (axillary) between 36.5°C and 37.0°C.

638  
639 The esophageal temperatures of all infants will be monitored closely on an ongoing basis  
640 to evaluate overshoot, depth of overshoot and time to equilibration. In addition, decreases  
641 of temperature following the initial overshoot and following equilibration will be  
642 monitored on an on-going basis. The type and timing of sedatives, analgesics and  
643 anticonvulsants will be recorded; use of these medications will be based on site practices.  
644

645 **4.7 Algorithm to prevent decreases of temperature to less than 31.0°C:** Infants  
646 assigned to 32.0°C arms of the study will have the target temperature set at 33.5°C  
647 initially. Once equilibration with 33.5°C is achieved (after overshoot) then the target will  
648 be reset to 32.0°C. All temperatures recorded  $< 32.0$ °C will be reviewed on an on-going  
649 basis.

650  
651 **4.8 Discontinuation of Hypothermia:** Infants will exit the assigned hypothermia  
652 intervention arm of the study if any of the following occur: parents withdraw consent,  
653 neonatologist withdraws consent or infant requires ECMO. Discontinuation of  
654 hypothermia for a serious adverse event requiring therapy (one or more of the following:  
655 cardiac arrhythmia, persistent acidosis, major thrombosis or bleeding or extensive skin  
656 breakdown) will be at the discretion of the attending physician after consultation with the  
657 study/site PI. If hypothermia is discontinued, rewarming will occur at 0.5°C per hour with  
658 further management per usual care at the site. The infant will continue to be part of the  
659 study as per intent-to-treat study protocol (unless parents explicitly withdraw permission  
660 to use any data).

661  
662 **4.9 Withdrawal of Support or Limitation of Care:** Decisions made with the family to  
663 limit or withdraw care will be documented. If the Study PI is the attending physician, a  
664 neonatologist other than the Study PI is encouraged to participate in these discussions. A  
665 neurological examination will be performed on the day support is withdrawn.  
666

667 **4.10 Post Randomization Exclusion of Infants:** The study is designed as intent-to-  
668 treat, and therefore infants will not be excluded after randomization.

669  
670 **4.11 Safety Monitoring of Control and Experimental Infants:**

- 671 a. Skin, esophageal, axillary, and servo set point temperature will be monitored  
672 every 15 minutes for the first 4 hours, every hour up to 12 hours, followed by  
673 every 4 hours during the maintenance phase of cooling and every 2 hours during  
674 the rewarming phase until normothermia is achieved.
- 675 b. Metabolic status: serum electrolytes will be monitored as per clinical routine.

- 676 c. Respiratory status: blood gases will be monitored every 4 to 6 hours. Since  
677 lower target temperatures (< 33.5°C) may be associated with risk of pulmonary  
678 hypertension, more frequent gas measurements may be required.
- 679 d. Cardiovascular: heart rate, blood pressure and use of inotropic agents will be  
680 recorded at baseline and every 4 hours throughout the study period. The risk of  
681 cardiac arrhythmia may be increased at < 33.5°C hence risk will be monitored  
682 along with treatment for arrhythmia. Echocardiograms will be performed as per  
683 site practice.
- 684 e. Renal status: urine output and body weight will be recorded daily during the  
685 intervention interval. Serum BUN and creatinine will be obtained at baseline  
686 and daily as per clinical routine.
- 687 f. Neurological status: To monitor for possible sagittal sinus thrombosis, a subset  
688 of infants will require a cranial sonogram performed within 48-72 hours  
689 following the end of the intervention period. Neurological examinations will be  
690 performed at baseline, following study intervention, pre-discharge and at time  
691 of withdrawal of support. The presence of seizures at baseline, during  
692 intervention and during rewarming will be recorded. All infants with clinical  
693 seizures will have EEG evaluations performed.
- 694 g. Hematological: Platelet counts will be obtained daily. PT/PTT will be obtained  
695 per clinical routine or if bleeding is suspected based upon clinical symptoms or  
696 an unexplained fall in hematocrit by more than 10%. Complete blood counts  
697 will be monitored as per clinical routine, including white blood counts and  
698 absolute neutrophil counts because of potential risk of infection. Since increased  

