### 5.3 Monitoring of Safety for the Trial:

- The protocol will be reviewed by the Institutional Review Board of each participating institution.
- The first interim analysis for safety will be conducted after 40 infants are enrolled (10 in each arm of the factorial design). Enrolment will be temporarily halted while the DSMC reviews the first interim analysis for safety and will be resumed only after the DSMC, on review of this data, is convinced that recruitment may commence.
- Following approval of the DSMC, the temperature data on the infants in the intervention arm of the study will be monitored by the PI and Subcommittee on an ongoing basis to document drops of temperature below target and plans to minimize this complication will be developed. There will be increased vigilance looking for potential complications of a greater depth of hypothermia on cardiac function, increased infection rates, increased bleeding or effects of increased viscosity.
- Serious adverse events will be reported on the MedWatch form to RTI. After the initial interim analysis for safety, serious adverse events will be compared between the treatment groups using sequential analysis methods after every 25 infants have been accrued into the trial. The 2 events that will be monitored include *arrhythmia* requiring therapy (excluding sinus rhythm or mechanical line-placement as a cause) and *major bleeding or thrombosis*. Neonates will be monitored with daily platelet counts and coagulation profile/CBC as clinically indicated. On-going masked central reading of cranial MRI will be undertaken once the MRI secondary study is approved, for evidence of CNS infarct/hemorrhage that is higher than the frequency noted in the NRN study evaluating cranial MRI among infants in the whole body hypothermia for neonatal HIE. The computed statistic will be compared to Pocock boundaries that are constructed beforehand so that an overall alpha level of 5% is maintained. RTI will be responsible for reporting adverse events to the DSMC of the Network.
- All protocol deviations/violations will be monitored by RTI.
- RTI will prepare reports for presentation to the DSMC at periodic intervals.
- DSMC will be responsible for monitoring the safety of the trial. Pre-specified looks will occur at 25%, 50%, 75% and 100% of data accrual at the conclusion of the study intervention.

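### Clinical seizures are recorded over a window that is 48 hours longer in the 120-hour arms, which can bias the duration comparison of this secondary outcome against longer cooling

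*Protocol*

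**What the plan says.** Section 4.0 defines the duration factor: "A prospective comparison of 2 cooling durations (72 vs.120 hours".

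Section 4.11(f) gives the seizure recording rule: "The presence of seizures at baseline, during" "intervention and during rewarming will be recorded". The end of recording is thus tied to the end of each infant's own rewarming. Section 4.6 fixes how long rewarming takes: "At the completion of cooling, the control set point will be increased 0.5°C per hour until" the esophageal temperature has been at 36.5°C or above "C for four hours. Once achieved, the esophageal" probe comes out.

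Section 4.15 names clinical neonatal seizures as a secondary outcome, separately from adverse events, and gives no time limit. Section 5.2 analyzes binary primary and secondary outcomes by robust Poisson regression to give risk ratios adjusted for level of encephalopathy and site. It mentions no exposure time.

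Other safety items follow different rules:
- Renal monitoring is tied to the intervention interval ("urine output and body weight will be recorded daily during the" intervention interval), and liver tests are taken at baseline and at its end.
- Cardiovascular data and fat necrosis are followed through a study period that is not defined.
- Pneumonia and blood stream infection are also noted over the whole hospital stay.
- Hyperthermia is followed for the first 10 days of life (section 4.12), and MRI is done at 7 to 14 days.
- For the two events monitored sequentially under section 5.3 (arrhythmia needing therapy; major bleeding or thrombosis), no window is stated.

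**The concern.** When the length of treatment is the randomized factor, a recording window defined by treatment phase differs by arm. A seizure at hour 100 in a 72-hour infant falls outside the rule in 4.11(f); the same seizure in a 120-hour infant is counted. If longer cooling had no effect on seizures, the 120-hour arms could still show more of them because they were watched for longer. A reader of the results could then take a difference in observation time for a harm of one of the two factors under test.

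This is a rule about what is collected, so a later analysis choice can repair it only in part. If seizure times are captured, both arms could be cut at about 82 h, but that discards the later hours in which the two durations differ.

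**Working it through.** **The plan's own figure.** Section 5.1 gives 363 per margin. With 37.5% vs 27.5%, two-sided 5%, 80% power, pooled variance and no continuity correction, n = 344 per margin. Then 344 / 0.95 = 362.1, rounded up to 363, or 726 in total. The figure reproduces and is not in dispute; 363 is used below.

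**Window length.** Hours = cooling + (36.5 − target) / 0.5 + 4, from sections 4.0 and 4.6.

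| Target | 72-hour arm | 120-hour arm | Difference | Ratio |
|---|---|---|---|---|
| 33.5°C | 72 + 6 + 4 = 82 h | 120 + 6 + 4 = 130 h | 48 h | 1.59 |
| 32.0°C | 72 + 9 + 4 = 85 h | 120 + 9 + 4 = 133 h | 48 h | 1.56 |

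This assumes that core temperature follows the set point during rewarming. A lag would lengthen both windows alike and leave the 48 h unchanged. Averaged over depth, the margins compare 83.5 h with 131.5 h.

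**Spurious risk ratio with no true effect of duration.** Let p be the risk over the shorter window, h = −ln(1 − p) / 83.5 the average hazard in it, and f the hazard in the extra 48 h as a fraction of h. The risk counted in the 120-hour arms is q = 1 − (1 − p) × exp(−f × h × 48), and the spurious risk ratio is q / p. The protocol gives no expected post-randomization seizure rate, so p and f are assumptions.

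Example with p = 10% and f = 1: h × 48 = 0.10536 × 48 / 83.5 = 0.06057, so q = 1 − 0.90 × 0.94123 = 15.3% and the ratio is 1.53.

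| p (72-hour arms) | f = 1 | f = 0.5 | f = 0.25 | f = 0.1 | f = 0 |
|---|---|---|---|---|---|
| 5% | 1.55 | 1.28 | 1.14 | 1.06 | 1.00 |
| 10% | 1.53 | 1.27 | 1.14 | 1.05 | 1.00 |
| 20% | 1.48 | 1.25 | 1.13 | 1.05 | 1.00 |
| 30% | 1.43 | 1.23 | 1.12 | 1.05 | 1.00 |

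**Chance of a nominally significant excess in the 120-hour margin.** This is for one two-sided 5% test of two proportions with 363 per margin; 2.5% is expected in that direction when there is no bias.

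| p | f = 1 | f = 0.5 | f = 0.25 | f = 0.1 |
|---|---|---|---|---|
| 5% | 33% | 13% | 6% | 4% |
| 10% | 57% | 21% | 9% | 4% |
| 20% | 85% | 36% | 13% | 5% |
| 30% | 95% | 50% | 17% | 6% |

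With a common window the length ratio is 1.00, and the spurious risk ratio is 1.00 for every p and f.

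**The case against.** The strongest reply has four parts.

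*Timing.* If seizures cluster early, little is counted in the extra 48 h. Section 2.8 says that seizures during rewarming were not seen in the two large earlier trials. This stands as a limit on the size of the bias. It does not remove the bias, because the same section cites rebound seizures on rewarming in clinical practice. Section 2.6 compares seizures at baseline and at 24, 48 and 72 h in the network's earlier trial but gives no counts from which a late hazard could be set.

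*True effect or bias.* Seizures caused by 48 more hours of cooling are a real consequence of the strategy. That is right: only background seizures in the extra hours are bias, and the calculation covers only those.

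*Pooling and other documents.* Section 4.11(f) names three phases and does not say that they are summed. The analysis plan or the manual of operations, neither of which is shown, may set a common window, and EEGs in infants with clinical seizures may be another source. This stands in part. If post-rewarming seizures are collected elsewhere in all arms, the problem disappears; the protocol's own recording rule does not provide for that.

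*Reach.* A reader might infer that acute adverse events in general are counted over intervention plus rewarming, so that the safety hypothesis in section 4.2 ("No increase in acute adverse events among infants cooled for 120 hours") and the sequential comparison in section 5.3 ("serious adverse events will be compared between the treatment groups using sequential analysis methods after every 25 infants have been accrued into the trial") are biased and an arm could be closed in error. The protocol does not support this. Section 4.15 lists seizures apart from adverse events, section 5.3 monitors only arrhythmia and major bleeding or thrombosis, and neither of these has a stated window that depends on arm. The renal and liver items tied to the intervention are routine measurements, not the compared events. The percentages above are also single-test figures, not probabilities of crossing a Pocock boundary.

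**Conclusion.** The point holds for clinical seizures. As written, their recording window is 48 h longer in the 120-hour arms, and the outcome falls under a risk-ratio analysis with no adjustment for observation time. The bias is against longer cooling or absent; counting extra background events cannot favor longer cooling. Its size is not known. The spurious risk ratio runs from 1.00 (no late seizures) through about 1.05 (late hazard one tenth of early) to about 1.5 (constant hazard, assumed risks of 5 to 20%). It would therefore be wrong to say that the 120-hour arms will show a false excess; they can.

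For the other acute adverse events the supportable point is narrower: the window, or the study period, is left undefined. Severity is moderate. A secondary outcome of one factor is affected. The primary outcome at 18 to 22 months is not, and the windows differ by only 3 h between depths (85 / 82 = 1.04).

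**What to change.** In section 4.11(f), record clinical seizures with date and time in all four cells over one common window from randomization, whatever the assigned duration. The window should cover 120 h of cooling plus rewarming and the 4-hour hold. An example is 0 to 144 h, which leaves 11 h beyond the longest computed window of 133 h. Name that window in section 4.15 as the one used for the between-arm comparison, and keep the counts by phase as descriptive.

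Apply the same common window to the acute adverse events compared under sections 4.2 and 5.3, and define the study period used in section 4.11.

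The cost is changed protocol and case-report-form wording and about two more days of chart abstraction in the 72-hour arms. No extra tests and no change in care are needed. One limit remains: bedside observation may be less intense once cooling has stopped, so a common window equalizes the recording time but not necessarily the closeness of observation. The change has to precede data collection to be fully effective.
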